#### 9.4.1 GENERAL APPROACH

Details of the data analysis for this study will be provided in the Statistical Analysis Plan (SAP), which will be finalized prior to database lock.

Unless otherwise specified, the last value obtained prior to infusion of study medication (Day 1) will be used as the baseline value. If a baseline measurement is missing, and a screening value available, the screening value will be utilized as Baseline instead.

#### 9.4.2 SAFETY ANALYSES

##### 9.4.2.1 LABORATORY EVALUATIONS, VITAL SIGNS AND ECG

Laboratory evaluations, vital signs, and ECGs will be analyzed for the Safety Set for observed cases. Descriptive statistics will be presented by cohort and treatment at each time point: change from Baseline in vital signs, serum chemistry, hematology, and urinalysis. For laboratory data, changes between the Baseline or, if missing, screening value and each posttreatment assessment may be presented in shift tables or using other summaries as detailed in the SAP. Assessment of liver-related changes will include:

- 3  $\times$ -, 5  $\times$ -, 10  $\times$ -, and 20  $\times$  ULN elevations of AST, ALT, and either ALT or AST
- Any elevations of bilirubin: elevated total bilirubin to  $>2 \times$  ULN
- Any elevations of ALP  $>1.5 \times$  ULN
- Elevation of AST or ALT ( $>3 \times$  ULN) accompanied by elevated bilirubin ( $>1.5 \times$  ULN,  $>2 \times$  ULN)
- Elevation of AST or ALT in temporal association with nausea, vomiting, anorexia, abdominal pain, or fatigue
- Any liver-related deaths and liver-related treatment discontinuations.

For ECG parameters, descriptive analysis and shift tables from predose will be performed. Further concentration QT analysis (eg, time-matched QT, and QTc analyses for XTMAB-16 and

placebo may be evaluated, including effect of XTMAB-16 concentration on QTc, and categorical analyses) and will be defined in a finalized SAP.

#### 9.4.2.2 ADVERSE EVENTS

Safety variables will be analyzed for all study participants in the Safety Set.

Adverse events will be coded by system organ class (SOC) and preferred term (PT) using the Medical Dictionary for Regulatory Activities (MedDRA) version 23 or higher.

The frequency of all AEs during the study will be presented for each cohort and treatment separately by SOC and PT. The data will be displayed as the number of participants experiencing the AEs, percentage of participants, and the number of events.

All TEAEs (defined as those AEs with an onset date/time on or after the start of infusion on Day 1 to end of safety follow-up), serious and nonserious, including deaths, will be tabulated and listed. Laboratory safety parameters that are reported as AEs will also be tabulated and listed.

#### 9.4.2.3 IMMUNOGENICITY

Anti-drug antibodies and nAb at each sampling time will be summarized with descriptive statistics (N, mean, SD, coefficient of variation [CV], geometric mean, geometric CV, median, minimum, and maximum) for each dose.

If ADA or nAb are detected, a direct link model may be used to describe the relationship between the serum concentration of XTMAB-16 and ADA or nAb levels, as AUC and time point concentration measurements to explore the time-dependence.

### 9.4.3 PHARMACOKINETICS

The PK analysis will be conducted for patients who have sufficient plasma concentration data to facilitate the calculation of at least one PK parameter and had no important protocol deviations affecting the PK variables as confirmed during a pre-analysis review of the data before database lock. The PK parameters will be calculated from the plasma concentration-actual time profiles. The non-compartmental analysis will be performed using Phoenix® WinNonlin® Software version 8.0 or higher (Certara, LP).

#### 9.4.3.1 SERUM CONCENTRATION-TIME DATA

Individual serum concentrations of XTMAB-16 at each PK sampling time (predose, at completion of infusion, and all other timepoints after the start of infusion) will be summarized with descriptive statistics (N, mean, SD, CV, geometric mean [gMean], geometric coefficient of variation [gCV], median, minimum, and maximum) for each dose. For descriptive statistics of the concentration-time data summaries, the nominal times (ie, planned times) will be used.

Figures for individual serum concentration of XTMAB-16 versus time profiles will be generated on regular and semi-log scales with mean for each dose. Figures for mean  $\pm$ SD serum concentration of XTMAB-16 versus time profiles will be generated on regular and semi-log scales together for all doses.

#### 9.4.3.2 PHARMACOKINETIC PARAMETERS

For determination of PK parameters, the actual sampling times (taking into account the actual dates and times) will be used. The following PK parameters will be obtained:  $C_{max}$ ,  $t_{max}$ ,  $AUC_{0-t}$ ,  $AUC_{0-\infty}$ , %  $AUC_{0-\infty}$ , CL,  $t_{2/1}$ ,  $\lambda_z$ ,  $V_z$ ,  $V_{ss}$ , and MRT. Individual dose-normalized parameters for  $C_{max}$ ,  $AUC_{0-t}$ , and  $AUC_{0-\infty}$  will also be summarized in terms of dose-normalized  $C_{max}$ ,  $AUC_{0-t}$ , and  $AUC_{0-\infty}$  ( $C_{max,norm}$ ,  $AUC_{0-t,norm}$ , and  $AUC_{0-\infty,norm}$ , respectively). Individual PK parameters of XTMAB-16 will be summarized with descriptive statistics (N, mean, SD, CV, gMean, gCV, median, minimum, and maximum) for each dose.

Dose proportionality will be evaluated for these PK parameters, viz.  $C_{max}$ ,  $AUC_{0-t}$ , and  $AUC_{0-\infty}$  by the power model (PK parameter =  $\alpha \bullet dose^{\beta}$ ). The power model will be fit on the log-transformed linear scale:  $\log(\text{PK parameter}) = \log(\alpha) + \beta \bullet \log(\text{dose})$ . An estimate of unity for  $\beta$  will indicate perfect dose linearity.

Details of the PK analysis, including PK Tables, Listings, and figures, will be provided in the SAP.

#### 9.4.4 BIOMARKER ANALYSIS

Biomarkers (ACE, sIL-2R, IL-6, and sTNF $\alpha$ ) at each sampling time (predose, at completion of infusion, and postinfusion timepoints) will be summarized with descriptive statistics (N, mean, SD, CV, geometric mean, geometric CV, median, minimum, and maximum) for each dose. Percent change from Baseline over time and total change from Baseline will be analyzed.

Details of the biomarker analysis will be provided in the SAP.

##### 9.4.4.1 BIOMARKER-CONCENTRATION-TIME DATA

All subjects without any major deviations related to study drug administration and for whom any biomarker (or effect) data are available will be included in the biomarker analysis. However, subjects being included in this population and having received only placebo will also be included as part of this data set.

Details of the biomarker analysis will be provided in the SAP.

##### 9.4.4.2 PHARMACOKINETIC AND BIOMARKER RELATIONSHIP

The relationship between each biomarker concentration and XTMAB-16 concentration collected at the same time point may be graphically displayed for individual subjects, and for mean data for each dose. In addition, these figures will also be generated for each biomarker with all the data pooled across all the doses.

Details of the PK and biomarker relationship analysis will be provided in the SAP.

#### 9.4.4.3 BIOMARKER PARAMETERS

These biomarker (or effect) parameters will be obtained, if data permit: area under the effect-time curve (AUEC), maximum observed effect ( $E_{max,obs}$ ), and time to reach maximum observed effect ( $t_{E_{max,obs}}$ ). The overall results of the biomarker assessments will determine whether these specific analyses will be performed.

If applicable, a PK/PD direct link model may be used to describe the relationship between biomarker levels and the XTMAB-16 concentrations at each time.

Details of the biomarker analysis will be provided in the SAP.

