## 4.2 SCIENTIFIC RATIONALE FOR STUDY DESIGN

The design of this Phase 1, SAD clinical trial is similar to other FIH studies evaluating TNF $\alpha$  inhibitors.

Based on TK results in the 6-week, GLP, toxicology study in hTNF $\alpha$  transgenic (TgTC) mice, the half-life ( $t_{1/2}$ ) of XTMAB-16 ranged from 9.4 days (226.9 hr) at 10 mg/kg to 13.6 days (327.2 hr) at 40 mg/kg, which is comparable to the half-life of 10 mg/kg of infliximab in humans of 13.9 days (335.1 hr). Approximately 90% of XTMAB-16 after a single dosing is expected to be eliminated from the system in 8 weeks. Therefore, the 8-week study duration is considered adequate to support safety and PK, biomarker, and immunogenicity analyses.

In support of the effect of XTMAB-16 on TNF $\alpha$ , additional biomarkers associated with TNF $\alpha$  activity and sarcoidosis have been selected for investigation in this first-in-human (FIH) study. The biomarkers selected for this study are sIL-2R, ACE, TNF $\alpha$ , and IL-6. ACE is a common biomarker used in the diagnosis of sarcoidosis. sIL-2R is a surrogate marker for T cell activation, is significantly elevated in sarcoidosis patients, and has been shown to have a high and superior sensitivity and specificity, compared to ACE, for diagnosing sarcoidosis in patients. IL-6 is elevated in patients with sarcoidosis and may be involved in the initiation and maintenance of alveolitis by activating and causing the proliferation of T cells. TNF $\alpha$  induces IL-6 through the nuclear factor k B pathway and, thus, inhibition of TNF $\alpha$  through XTMAB-16 is likely to be reflected in a change in IL-6 circulating levels. These biomarkers are normally low or undetectable in healthy participants. However, as XTMAB-16 is intended for use in patients with pulmonary sarcoidosis (in whom these biomarkers are likely to be elevated), XTMAB-16 is expected to influence the levels of these biomarkers in patients. Measuring these biomarkers in healthy participants will establish relative baseline levels of these biomarkers for comparison in later trials in patients.

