## 9 STATISTICAL CONSIDERATIONS

### 9.1 STATISTICAL HYPOTHESES

Hypothesis testing will not be conducted for this study.

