### 9.2 SAMPLE SIZE DETERMINATION

The selection of 24 participants (12 per cohort) was based on feasibility and precision around the estimates for target variables associated with the primary and secondary endpoints. No sample size calculation was performed.

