3.2.8 Biomarker Variables

Absolute and percent change from baseline in the following biomarkers will be analyzed.

- Angiotensin converting enzyme (ACE)
- soluble IL-2 receptor (sIL-2R)
- Interleukin 6 (IL-6)
- soluble TNF α (sTNF α)

Biomarker samples will be corrected for biomarker analysis at pre dose (Hour 0), and at 8 hours on Day 1, 24 hours (Day 2), 50 hours (Day 3), 74 hours (Day 4), 170 hours (Week 2, Day 8), 338 hours (Week 3, Day 15), 674 hours (Week 4, Day 29), 1010 hours (Week 6, Day 43), 1346 hours (Week 8, Day 57), and 1682 hours (Week 10, Day 71) post infusion of XTMAB-16 or placebo. All sampling time points after time T refer to time from the start of infusion.

Unless otherwise stated, derivation of biomarker parameters will be the responsibility of Clinical Pharmacology, Modeling and Simulation (CPMS, formerly Quantitative Clinical Development (QCD), Parexel International. The following biomarker parameters, if data permit, will be determined for XTMAB-16 in serum following single IV dose administration:

Table 3 Biomarker Parameters after Single Dose Administration

Parameter	Definition
AUEC	Area under the effect-time curve
E _{max,obs}	Maximum observed effect
t _{E_{max,obs}}	Time to reach maximum observed effect

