4.12.2 Biomarker Analysis

Biomarker analysis of ACE, sIL-2R, IL-6, and sTNF α will be based on Biomarker Set.

All participants without any major deviations related to study drug administration and for whom any biomarker (or effect) data are available will be included in the biomarker analysis. However, participants being included in this population and having received only placebo will also be included as part of this data set.

Percent change from Baseline over time and total (absolute) change from Baseline will be analyzed.

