4.12.2.1 Biomarker Concentration-Time Data

Biomarkers (ACE, sIL-2R, IL-6, and sTNF α) at each biomarker sampling times will be summarized with descriptive statistics (N, mean, SD, CV%, geometric mean, geometric CV%, median, minimum, and maximum) for treatment, day, and nominal timepoint.

For presentation in biomarker summary tables if less than 4 significant digits, all summary statistics will be tabulated to one more significant digit compared to the source data, otherwise up to a maximum of 4 significant digits, with exception of N, and n that will be presented as whole numbers, CV% and geometric CV% that will be presented to 1 decimal place.

To visualize the comparison between treatment, the following descriptive biomarker graphs will be generated. For each figure participants belonging to each category will be shown on the same plot with separate figures for each level of dose. Figures will be displayed in unique line and marker color, line style and marker for each plot in the graph. For all biomarker-time plots, linear scale will be used for both x-axis and y-axis. The following plots will be generated for each of biomarkers.

- Figure xx.1: Individual Biomarker-Time Profiles (Absolute change and percent change from Baseline) (Biomarker Set)
- Figure xx.2: Mean (\pm SD) Biomarker-Time Profiles (Absolute change and percent change from Baseline) by dose and placebo groups (Biomarker Set)

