4.12.2.2 Biomarker Parameters

These biomarker (or effect) parameters will be obtained, if data permit: area under the effect-time curve (AUEC), maximum observed effect ($E_{max,obs}$), and time to reach maximum observed effect ($t_{E_{max,obs}}$). The overall results of the biomarker assessments will determine whether these specific analyses will be performed.

Biomarker parameters will be provided by CPMS group. Biostatistics group will use this data for calculation of biomarker parameter summary statistics tables.

Biomarker parameters will be calculated by non-compartmental analysis methods from the biomarker-time data using Phoenix® WinNonlin® (Version 8.2) or higher following these guidelines:

- Actual sampling times relative to the start of infusion rather than nominal times will be used in the calculation of all derived biomarker parameters.
- There will be no imputation of missing data.

Biomarker parameters will be listed by treatment and subject for the Biomarker Set. Biomarker parameters will be summarized by different dose and placebo groups.

For presentation in biomarker parameter summary tables if less than 4 significant digits, all summary statistics will be tabulated to one more significant digit compared to the source data, otherwise up to a maximum of 4 significant digits, with exception of N, and n that will be presented as whole numbers, CV% and geometric CV% that will be presented to 1 decimal place.

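### Protocol 9.4.4.3 and SAP 4.12.2.2 let the biomarker results decide, by no stated rule and not necessarily blind, whether AUEC, Emax,obs and tEmax,obs are derived, which leaves room for selective reporting

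*Protocol*

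**What the plan says.** Two conditions govern the three biomarker parameters.

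- **Computability.** SAP 3.2.8 states: "The following biomarker parameters, if data permit, will be determined for XTMAB-16 in serum following single IV dose administration". Protocol 9.4.4.3 and SAP 4.12.2.2 carry an equivalent condition.
- **Results.** Protocol 9.4.4.3 then adds: "The overall results of the biomarker assessments will determine whether these specific analyses will be performed". SAP 4.12.2.2 has the same sentence and adds no rule. Neither document says what result counts, in which direction, who decides or when.

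SAP 3.1.2 makes treatment codes available after database lock. SAP 4.12.2.1 plans summaries by treatment and mean profiles by dose and placebo. Nothing prevents the decision from being taken with these in view.

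The rest of the biomarker analysis is unconditional. SAP 4.12.2 says "Percent change from Baseline over time and total (absolute) change from Baseline will be analyzed", and under SAP 4.12.2.1 all four markers "at each biomarker sampling times will be summarized with descriptive statistics". If the parameters are derived, SAP 4.12.2.2 says "Biomarker parameters will be summarized by different dose and placebo groups". They are not among the endpoints in Protocol Section 3 or SAP 3.2.1, which list absolute and percent change from Baseline. Protocol 9.1 states: "Hypothesis testing will not be conducted for this study".

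**The concern.** A condition on whether a quantity can be calculated is ordinary. A condition on what the results look like is different, because the decision to report then depends on the data being reported. With 9 participants per dose and 6 on placebo, sizeable differences arise by chance. If parameters tend to appear when the profiles look responsive, the published AUEC and Emax,obs values will on average overstate the effect. The plan does not ask for the reason for an omission to be reported, so a reader could not tell failure to calculate from lack of interest in the result. In a study without tests, the descriptive estimates are the biomarker output, so their size matters.

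**Working it through.** The plan has no figure to reproduce. Protocol 9.2 states "No sample size calculation was performed", and no biomarker variability is given. The calculations below only show what different readings of the gate would do.

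**Inputs from the documents.** 9 active per dose and 3 placebo per cohort (Protocol Table 2), so 3 + 3 = 6 pooled; four markers and ten post-dose sampling times (SAP 3.2.8).

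**Assumptions.** SD of 1 per participant, independent markers, the same quantity inspected and reported, and a cut-off that the plan does not supply.

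**A. No true effect, two-sided gate at 0.8 SD (200,000 simulated trials)**

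1. The standard error of one dose-placebo difference is √(1/9 + 1/6) = 0.527 SD.
2. For each marker, take the larger of the two absolute dose-placebo differences. With no selection it averages 0.56 SD.
3. At least one of the four markers passes in 62% of trials. That is a chance of 0.214 per marker: 1 − (1 − 0.214)⁴ = 0.618. With cut-offs of 0.5 and 1.0 SD the rates are 95% and 34%.
4. Markers selected one by one: those that pass average 1.04 SD.
5. One decision for all four, triggered by any marker passing: markers that do not pass average (0.56 − 0.214 × 1.04)/0.786 = 0.429. No marker passes in 0.382 of trials. The average where all four are reported is (0.56 − 0.382 × 0.429)/0.618 = 0.64 SD.
6. The mean signed difference is about 0 in both cases, because chance differences in the two directions cancel.

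If the markers are positively correlated, the figure in step 5 moves towards that in step 4; with perfect correlation the two coincide.

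**B. True effect 0.3 SD, one dose, one-sided gate at 0.8 SD**

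- z = (0.8 − 0.3)/0.527 = 0.949; normal density 0.254; upper tail 0.1714.
- One by one: 0.3 + 0.527 × 0.254/0.1714 = 1.08 SD.
- One overall decision: markers that do not pass average 0.3 − 0.134/0.8286 = 0.138, and none passes with probability 0.8286⁴ = 0.4714. This gives (0.3 − 0.4714 × 0.138)/0.5286 = 0.44 SD.

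**C. AUEC over the ten sampling times, one marker, 9 v 6 (40,000 trials per setting)**

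AUEC is the trapezoidal time-average of change from Baseline. Entries are bias in the active-placebo difference in SD units; ranges cover within-participant correlation of 0.3 and 0.7.

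| Gate | True 0 | True 0.5 | True 1.0 |
|---|---|---|---|
| Mean difference >0.5 SD, effect direction | +0.64 to +0.73 | +0.26 to +0.36 | +0.04 to +0.11 |
| Any time point nominal p<0.05, effect direction | +0.35 to +0.68 | +0.15 to +0.38 | +0.03 to +0.15 |
| Gate unrelated to effect | about 0 | about 0 | about 0 |

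With a two-sided 0.5 SD gate and no true effect, signed bias is about 0 (0.01 or less), but the mean absolute difference rises from 0.27–0.36 to 0.64–0.72. With a true effect of 0.5 SD, the same two-sided gate gives +0.25 to +0.32.

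**The case against.** The strongest reply is that the sentence is only a feasibility clause. Protocol 4.2 says of these markers: "These biomarkers are normally low or undetectable in healthy participants". Flat or unquantifiable profiles would be a good reason not to derive an AUEC, and a gate unrelated to effect causes no bias. That reading is possible. But computability is already covered by the preceding condition, so on that reading the sentence is redundant and can be removed without loss.

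Other parts of the reply stand and limit the point.

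- A reader might infer that the parameters will be reported only when an effect appears, and so are biased upward. The text gives no direction and does not define which sign counts as an effect. With no true effect, a two-sided gate inflates absolute size, not the signed mean.
- A reader might infer that analysts will pick among the four markers. The text refers to overall results, which reads at least as naturally as one decision for the set. Most of the inflation in calculation A comes from marker-by-marker choice (1.04 v 0.64 SD).
- A reader might infer that a primary endpoint is gated, because SAP 3.2.1 lists biomarker change as primary. The listed endpoints are not gated; only the derived parameters are.
- Omission would not be invisible. SAP Table 3 names the parameters, and every marker's profile is tabulated and plotted. Of the three, only AUEC summarises the whole profile; Emax,obs is one extreme value and tEmax,obs its time.

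**Conclusion.** The point holds as a results-dependent analysis rule with no criterion and no requirement to decide blind. It permits selective reporting and could exaggerate the apparent effect size. The documents do not show that this will happen or in which direction.

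Under an assumed two-sided 0.8 SD cut-off, no true effect and independent markers, the larger absolute difference averages 0.64 SD under one overall decision and 1.04 SD under marker-by-marker selection, against 0.56 SD with no selection. With no true effect, signed bias needs a gate that favours one direction. With a directional gate it is material for small true effects and minor for large ones (calculation C).

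The consequence is modest. These are supportive derivations, the underlying change-from-Baseline data are reported in full, and there is no test whose error rate could be inflated. The change is still worth making because it costs almost nothing and closes the route.

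**What to change.** Delete the results sentence from SAP 4.12.2.2, and from Protocol 9.4.4.3 at the next amendment. Keep only the computability condition, and define it in the SAP before unblinding:

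- Derive and summarise AUEC, Emax,obs and tEmax,obs for all four markers, at both doses and pooled placebo, in every Biomarker Set participant whose profile allows it. Use the SAP 4.5 definition of the set, which includes placebo participants.
- State the minimum number of non-missing samples needed per profile.
- State how values below quantification enter the calculation. They should count as data and must not trigger exclusion. The SAP gives such rules for drug concentrations (4.10) but none for biomarkers.
- Report the number not calculable by marker and group.

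Do not substitute a threshold on the percentage of quantifiable samples pooled over treatments. Because 18 of 24 participants are active, a drug effect could itself fail such a rule. With all placebo samples quantifiable and 40% of active samples pushed below quantification, the pooled figure is 6/24 + (18/24) × 0.6 = 0.70. Any stronger suppression would fail a 70% threshold and remove the parameters.

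The cost is a short edit and a few more descriptive tables, some possibly uninformative.
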